#### **40. Methods that will be used to contact patients**

Telephone calls to the contact provided by the patient or by email.

#### **41. Statistical analysis (Description of the processing plan and presentation of the information. Include the justification of the statistical tests that will be used)**

The distribution of the variables will be evaluated with the Shapiro-Wilk test. Descriptive statistics will be used for the presentation of the variables, estimating averages and standard deviation for variables with normal and median distribution and interquartile range for variables with non-normal distribution. The prevalence and frequencies will be expressed in terms of percentage. The variables in each group will be compared by Student's T-test or U-Mann Whitney (as appropriate). Categorical variables will be compared by Fisher's exact test or Chi square analysis. A statistically significant difference with a value of  $P < 0.05$  will be considered. The statistical program SPSS version 21 will be used for data analysis.

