#### **42. Justification of the sample size (include the power of the study and the value of p that will be considered significant)**

For the calculation of the sample we consider (study on which we are based):

The calculation of the sample size was carried out taking as main outcome the body weight and considering the data of a study in which BMI and weight were evaluated. With these data considering a clinically significant difference, the sample size was calculated in 25 patients per group. A difference in weight 2kg, standard deviation of 2.5, alpha of 0.05 and power of 0.8 were used.

with the following formula:

$$n = 2S^2 (Z\alpha + Z\beta)^2$$

$$\Delta^2$$

Allowing to detect this difference with power of 80% (error  $\beta = 0.20$ ) and with an alpha error of 5%

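### The test and summary for body weight are left to a Shapiro-Wilk result on the trial data, although the trial is sized on a 2 kg difference in means

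*Protocol*

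**What the plan says.** Section 41 begins with a distribution check: "The distribution of the variables will be evaluated with the Shapiro-Wilk test". The summary follows from it: mean and standard deviation for normal variables, and "median distribution and interquartile range for variables with non-normal distribution" otherwise. The tests come next: "The variables in each group will be compared by Student's T-test or U-Mann Whitney (as appropriate"). The section gives no other criterion for what is appropriate, does not exempt weight, and names no fixed effect measure for it.

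Section 42, repeating section 27, bases the size of the trial on one outcome and one quantity: "The calculation of the sample size was carried out taking as main outcome the body weight", with these inputs: "A difference in weight 2kg, standard deviation of 2.5, alpha of 0.05 and power of 0.8 were used". The formula given is the one for comparing two means, and "the sample size was calculated in 25 patients per group". Section 39 lists weight among the main outcomes and plans three measurements, six weeks apart.

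**The concern.** The sample-size sections fix the question as a difference in mean weight, in kilograms. The analysis section leaves it open whether that quantity is tested. If Shapiro-Wilk rejects, section 41 leads to two medians and a rank-test P value. Mann-Whitney does not test a difference in means unless the two distributions have the same shape. The summary and test could also differ between the three weight measurements.

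At stake is whether the result for the sizing outcome can be set directly against the planned 2 kg, and whether its effect measure was fixed before the data were seen.

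**Working it through.** **Inputs from the protocol.** Difference 2 kg, standard deviation 2.5 (unit not given, taken as kg), alpha 0.05, power 0.80, 25 per group (section 42); significance at P < 0.05 (section 41).

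**Assumptions.** Section 41 gives no level for Shapiro-Wilk; 0.05 is assumed. It does not say whether the check is made per arm or on pooled data, so both are shown. It also does not say whether raw weight or change is checked. The distribution shapes below are assumed; the protocol gives none for weight.

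**Step 1: reproduce the stated size.** n = 2S²(Zα + Zβ)²/Δ² = 2 × 6.25 × (1.960 + 0.842)²/4 = 24.53, rounded up to 25. This matches. A one-sided alpha would give 20, so the stated figure is two-sided. Power at 25 per group is 0.807 by the normal approximation and 0.791 by the exact t-test.

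**Step 2: how often the rule leaves the t-test.** Simulation, 25 per arm, true shift 2 kg, standard deviation 2.5, 8,000 trials per shape:

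| Shape (same in both arms) | To Mann-Whitney, check per arm | To Mann-Whitney, check pooled |
|---|---|---|
| Normal | 9.6% | 4.8% |
| t, 5 df | 39.0% | 27.6% |
| Gamma, shape 4 | 60.1% | 46.4% |
| Lognormal, sigma 0.5 | 85.9% | 72.5% |

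A separate run of 6,000 trials per shape, checked per arm, gave 10% for normal, 48% for t with 4 df and 60% for gamma shape 4.

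**Step 3: error rates when both arms have the same shape.** The two-stage rule rejects as follows (per arm / pooled):

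| Shape | No difference | 2 kg difference | t-test alone, 2 kg |
|---|---|---|---|
| Normal | 0.053 / 0.052 | 0.786 / 0.787 | 0.789 |
| t, 5 df | 0.050 / 0.048 | 0.841 / 0.827 | 0.795 |
| Gamma, shape 4 | 0.055 / 0.049 | 0.829 / 0.821 | 0.791 |
| Lognormal, sigma 0.5 | 0.055 / 0.052 | 0.902 / 0.895 | 0.796 |

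The simulation error at a true 5% is √(0.05 × 0.95/8000) = 0.0024, so every value in the no-difference column is close to 5%. Power is not lost.

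**Step 4: equal mean weight, different shapes.** Here a test of means should reject about 5% of the time.

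- One arm skewed (lognormal), the other normal, per-arm check: two-stage rule 6.6%, t-test 5.0%; excess 1.6 points.
- One arm a responder/non-responder mixture (assumed: subgroups 4 to 6 kg apart, 20 to 50% in one of them), the other normal, 5,000 trials: two-stage rule 4.8 to 7.3% per arm or 4.6 to 5.9% pooled, t-test 4.7 to 5.8%. With the per-arm check the upper ends differ by 1.5 points.
- Opposite skew in the two arms, an extreme case, per-arm check: 14.3% against 6.0% (lognormal), 12.5% against 6.2% (gamma shape 2).

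**The case against.** Choosing between these tests by a normality check is common practice, and step 3 shows little operating harm: with equal shapes type I error holds, and the rank test gains power when tails are heavy. The link from Shapiro-Wilk to the choice of test is not stated word for word. An analysis plan that is not shown might fix the effect measure.

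The points on error rates and power stand, and they limit the finding. The others do not remove it. Shapiro-Wilk is the only criterion section 41 offers. The protocol itself fixes the data-dependent rule, and section 45 requires an amendment for departures from the statistical plan.

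Three stronger readings are tempting and are not supported:

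- A reader might infer that the trial could not report a kilogram difference with its interval. No interval is planned in section 41, and a rank test does not prevent a mean difference from being shown beside it.
- A reader might infer that the rule produces false positives too often, for example if some patients on three meals do very well and others abandon the plan. The mixture case in step 4 gives an excess of only about 1.5 points. Sections 36 and 38(c) also remove withdrawn and non-adherent patients, so those who abandon would largely be absent from the data.
- A reader might infer an error in sample size or power. Steps 1 and 3 show none.

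**Conclusion.** The point holds as a minor mismatch between design and analysis. For the outcome on which the trial is sized, the test and the reported summary are chosen by the observed data, while the sizing is for a difference in means.

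With a per-arm check at 0.05, the switch occurs in about 10% of trials even when data are exactly normal, and in about 40 to 60% under moderate non-normality. A pooled check gives about 5% for normal data and, with a true 2 kg shift, 28 to 46% for t with 5 df and gamma shape 4. These rates depend on the assumed level, the assumed shapes and the plain reading of section 41.

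The harm is to the estimand and to prespecification. The stated 25 per group reproduces. Type I error is near 5% when shapes agree and rises by 1 to 2 points when one arm is skewed or a mixture; only opposite skew produces a large excess.

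**What to change.** In section 41, exempt body weight from the distribution rule and name one comparison in advance, whatever Shapiro-Wilk shows: the difference between arms in mean weight change from baseline to week 12, with a 95% confidence interval, ideally adjusted for baseline weight. Change fits the hypothesis in section 11, which concerns weight loss. The final visit should be named explicitly, because section 13(a) gives 14 weeks where sections 13(f), 18 and 39 give 12; these must be reconciled. Mann-Whitney stays as a labelled sensitivity analysis.

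The change is to wording only, and 25 per group stands (power 0.81 by the normal approximation, 0.79 by the exact t-test). The price is some power relative to the rank test if weight change is heavy-tailed: about 0.80 against 0.88 for t with 4 df. With normal data the t-test is slightly ahead, 0.80 against 0.77. Fixing scales for the other variables, such as logarithms for skewed laboratory measures, is optional and not needed for this point.

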## **11. Hypothesis**

1. 1. Weight loss in the TC3 group (Three meal times) will be more significant than in the TC6 group (Six meal times).
2. 2. It will significantly improve glycemic variability in patients undergoing the TC3 regimen.

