## **12. Objetives**

### **Primary objetivo:**

Comparar el impacto en la variabilidad glucémica y pérdida de peso de un régimen alimenticio hipocalórico de tres tiempos (TC3) y un plan convencional de seis tiempos (TC6) en pacientes con DM2 y sobrepeso u obesidad.

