## **13. Methodology: General design.**

### a) Study design:

It is a simple blind randomized clinical trial (Information Analyst) in which a group of patients with DM2 and overweight or obesity will be subjected to a 3-course low-calorie diet (TC3), and another to a conventional hypocaloric regimen of 6 meal times (TC6) over a period of 14 weeks with the objective of evaluating the benefits, differences and impact on the health of patients, comparing weight loss, glycemic variability, HbA1c, glycemia, lipid profile , oxidative stress, FGF-21, Blood pressure and Hunger-Satiety level.

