## **26. Failure and success criteria**

Success: Corroborate that the effects of a TC3 diet are more beneficial than a conventional TC6 plan. To achieve this, patients should have better glycemic variability, lose more weight, improve fasting blood glucose, improve HbA1c, optimize their lipid level, improve oxidative stress markers and have better control of Hunger-Satiety.

Failure: That the effects of a TC3 diet be equal or less beneficial to the patient's health than a conventional TC6 plan.

**27. Sample size (please include the formula used for the calculation and the source of information on which the assumptions were based)**

a) Sample size

The calculation of the sample size was carried out taking as main outcome the body weight and considering the data of a study in which BMI and weight were evaluated. With these data considering a clinically significant difference, the sample size was calculated in 25 patients per group. A difference in weight 2kg, standard deviation of 2.5, alpha of 0.05 and power of 0.8 were used.

with the following formula:

$$n = 2S^2 (Z\alpha + Z\beta)^2$$

$$\Delta^2$$

Allowing to detect this difference with power of 80% (error  $\beta = 0.20$ ) and with an alpha error of 5%

**28. Description of the techniques, devices and / or instruments that will be used in the measurement (Including: special mechanical, electronic, cybernetic equipment)**

An RJL body composition analyzer with stadiometer will be used.

An ergonomic continuous fiberglass tape measure will be used to measure the circumference of the Seca201® brand body

For the continuous measurement of glucose and glycemic variability, the Medtronic Ipro2 Sensor will be used.

The blood samples will be labeled prior to their inclusion in the "Beckman GPKR Centrifuge" equipment to perform their centrifugation and to be able to separate serum samples, to obtain the laboratories and eppendorf containers will be stored, for each time, to be able to consult later before any situation of doubt Samples will be separated from the tubes to obtain the laboratories.

Beckman-Coulter equipment will be used for the analysis of samples corresponding to blood count.

The Hunger-Satiety scales of the Joslin Institute will be used.

Computing teams of the Department of Endocrinology will be occupied, which have Windows 8.1 pro operating system.

The Easy GV® Software will be used to calculate the glycemic variability indices.

SPSS V21 will be used for data capture and analysis.

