#### **38. Selection criteria**

- a) Inclusion criteria (It must include the definition of the age groups, sex and the severity of the condition that will be allowed in the study)
  - a) Individuals with type 2 diabetes
  - b) Less than 10 years of evolution

c) Age between 40 and 70 years
 
d) Both genders.
 
e) With oral treatment scheme (oral hypoglycemic agents).
 
f) With HbA1c <9%
 
g) With BMI <math>\geq 25</math> to <math><40</math> kg / m^2

b) Exclusion criteria

a) Individuals with another type of diabetes.
 
b) Use of insulin.
 
c) Evolution time of more than 10 years.
 
d) Hospitalization in the last 3 months
 
e) Disease with poor short-term prognosis (for example: cancer)
 
f) Acute infection or febrile syndrome
 
g) Chronic disease other than those to be evaluated, for example: HIV, rheumatic diseases, liver cirrosis
 
h) Pregnancy
 
i) Who do not wish to participate in the study

c) Elimination criteria

a) Men or women who do not wish to continue in the study
 
b) Individuals who do not tolerate the placement of the MCGI
 
c) Individuals who are not attached to the meal plan.
 
d) Individuals who do not respect the corresponding meal times during the study.

39. Outcome and variables

a) Main variables / outcomes to be measured
 
BMI (kg / m^2)
 
a) Weight
 
Glycemic variability, defined with the following indices:
 
a) MAGE (mean amplitude of glycemic excursions)
 
b) MODD (mean of daily differences)
 
c) CONGA-n
 
b) Secondary outcomes to be measured:
 
a) Fasting glucose
 
b) Triglycerides
 
c) Total Cholesterol
 
d) HbA1c
 
e) Oxidative stress
 
f) FGF21
 
g) Systolic and diastolic BP
 
h) Hunger-Satiety Scale
 
a) Frequency of measurements:

Three measurements will be made in a 12-week period with a 6-week interval between each measurement, however the sensor placed in visit 2 will be left for 7 days during which glucose measurements in the interstitial fluid will be obtained every 5 minutes.

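### The outcome and analysis sections do not tie the primary weight comparison to weight change from the pre-diet visit, although weight loss is evidently what is meant

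*Protocol*

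**What the plan says.** The aim is stated as weight loss in four places:

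- Section 11, first hypothesis: "Weight loss in the TC3 group (Three meal times) will be more significant than in the TC6 group".
- Section 12, primary objective: "Comparar el impacto en la variabilidad glucémica y pérdida de peso".
- Section 13, study design: "differences and impact on the health of patients, comparing weight loss, glycemic variability".
- Section 26, success criterion: "patients should have better glycemic variability, lose more weight, improve fasting blood glucose".

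The sections that fix the outcome, the sample size and the test use different terms:

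- Section 39 lists weight among the main outcomes, beside BMI and three glycemic variability indices. It gives no change score, reference measurement or primary time point.
- Sections 27 and 42 take body weight as the outcome for sizing: "A difference in weight 2kg, standard deviation of 2.5, alpha of 0.05 and power of 0.8 were used". The SD is not labelled.
- Section 41 gives the between-group analysis: "The variables in each group will be compared by Student's T-test or U-Mann Whitney (as appropriate". The choice follows a Shapiro-Wilk check.

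Section 16 has weight measured at the first visit, before the plan is prescribed, and again after each six-week period. It is not listed at the 15-day visit. Visit 1 is therefore the only described pre-diet weight.

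The end point in time is also stated in two ways. Section 13 has "over a period of 14 weeks with the objective of evaluating the benefits", whereas section 39 has "Three measurements will be made in a 12-week period with a 6-week interval between each measurement".

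**The concern.** Weight loss and weight are different variables with very different spread. Loss removes the stable differences between persons; raw final weight leaves them in the error term. The trial is sized on this outcome, yet the sections that define and test it do not say which variable enters the test. A t-test on change and a t-test on final weight would both comply with the wording of section 41, so the amendment procedure in section 45 would not separate them.

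An analysis of raw weight would very probably miss a true 2 kg effect, and section 26 counts equal benefit in the two groups as failure. A second, smaller matter is that the normality check can turn the comparison into a rank test. A rank test does not estimate the 2 kg mean difference on which the trial is sized.

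**Working it through.** **Inputs.** Difference 2 kg, SD 2.5 kg, alpha 0.05 and power 0.80 (section 42); 25 per group (sections 42 and 43); BMI 25 to under 40 (section 38). Assumptions, because the documents give no figure: raw-weight SD of 5 to 15 kg, equal at both times, and a height of 1.60 m for illustration.

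**Step 1, the plan's own figure.** With the formula in section 42, n = 2 × 2.5² × (1.960 + 0.842)² / 2² = 24.5, so 25 per group. This reproduces with a two-sided alpha; one-sided would give 20. Power at 25 per group is 81% by the normal approximation and 79% by the exact t calculation (48 df). The half-width of the 95% CI is 1.4 kg.

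**Step 2, what the 2.5 kg can be.** At 1.60 m the permitted BMI range runs from 25 × 2.56 = 64.0 kg to 40 × 2.56 = 102.4 kg. An SD of 2.5 kg is not plausible for raw weight over that span. It fits weight change or a baseline-adjusted residual. The documents do not say which.

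**Step 3, power under the two readings** (exact t, 25 per group, 2 kg):

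| Variable tested | SD (kg) | Power |
|---|---|---|
| Weight change | 2.5 | 79% |
| Raw final weight | 5 | 28% |
| Raw final weight | 8 | 14% |
| Raw final weight | 10 | 11% |
| Raw final weight | 12 | 9% |
| Raw final weight | 15 | 7% |

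The CI half-width for raw weight would be 2.84 kg at SD 5 and 8.53 kg at SD 15, against the 2 kg sought.

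**Step 4, what adjustment adds over a t-test on change.** Let ρ be the correlation of first and final weight.

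- The variance of change is 2 × SD² × (1 − ρ). Setting it to 2.5² gives ρ = 1 − 2.5² / (2 × SD²), which is 0.951 at SD 8 and 0.986 at SD 15.
- The ANCOVA residual variance is SD² × (1 − ρ²), so the residual SD is 2.47 to 2.49 kg.
- The saving over change is 1 − (1 + ρ)/2, that is 2.4% at SD 8 and 0.7% at SD 15.
- ANCOVA power (47 df) is 79 to 80%.

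If 2.5 kg is instead the residual SD, the SD of change is 2.51 to 2.53 kg. ANCOVA power is then 79% and a t-test on change has 78 to 79%. The planned 25 per group is adequate either way.

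**Step 5, the rank-test branch.** In 40,000 simulated trials with normally distributed change (SD 2.5 kg), Mann-Whitney had 77% power and the t-test 79%. The loss is mainly the mean difference and its CI.

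**Step 6, the final time point.** The intervals in section 16 add to (15 + 42 + 42) / 7 = 14.1 weeks, or 15.1 weeks if the first six weeks start after the seven sensor days. Section 39 gives 12 weeks and section 13 gives 14.

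**The case against.** The strongest reply is that the protocol, read as a whole, already answers the question. Four sections speak of weight loss, and the 2.5 kg SD makes sense only for change or something close to it. An analyst who compared raw final weight would contradict all of that. A t-test on weight loss is valid in a randomised trial and already uses the visit-1 weight, since loss is the difference from it. ANCOVA then adds about 1 to 2% of variance. The analyst is blinded (section 13), and the choice between change score and covariate adjustment is often left to a statistical analysis plan, which may exist here but is not shown.

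Most of this stands. It means the point is about wording in the outcome and analysis sections, with no error in the sample size and no invalid test. A reader might infer that the trial is underpowered, or that the protocol plans to compare raw weights. The documents do not support either: the low powers belong to a reading that the stated aims contradict, and they rest on assumed SDs.

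What does not fall away is that section 41 is the protocol's own plan and names a specific unadjusted test. Section 45 measures deviations against that plan, and no sentence in sections 39, 41 or 42 connects it to weight loss.

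**Conclusion.** The point holds as an ambiguity in the outcome on which the trial is sized, and it should be closed. On the evident reading, change from pre-diet weight, planned power is kept at about 80% and 25 per group stands. On the literal alternative that the text also permits, power for 2 kg would be about 7 to 28%. That range depends on an assumed raw-weight SD of 15 down to 5 kg, but power is far below 80% across all of it.

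The benefit of the change lies in ruling out that alternative and in fixing an estimate with a CI. It does not lie in a material power gain: ANCOVA saves only 0.7 to 2.4% of variance over a t-test on change, for weight SDs of 15 down to 8 kg. The rank-test branch and the missing SD label change the numbers very little.

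**What to change.** - **Sections 39 and 41:** define the primary weight outcome as change from the visit-1 (pre-diet) weight to the final visit. Name that visit once the 12-week and 14-week statements have been reconciled.
- **Section 41:** analyse this outcome by ANCOVA with group and visit-1 weight in the model, and report the adjusted mean difference with its 95% CI. With baseline in the model, analysing change or final weight gives the same group difference. Keep this analysis primary whatever the Shapiro-Wilk result, with any rank test on change as a sensitivity analysis only.
- **Sections 27 and 42:** state that the 2.5 kg SD refers to weight change, if the source study confirms it; otherwise state what it does refer to.

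The cost is a few sentences and one standard procedure in the SPSS version already named. The sample size stays at 25 per group, and no additional measurements are needed.

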#### **42. Justification of the sample size (include the power of the study and the value of p that will be considered significant)**

For the calculation of the sample we consider (study on which we are based):

The calculation of the sample size was carried out taking as main outcome the body weight and considering the data of a study in which BMI and weight were evaluated. With these data considering a clinically significant difference, the sample size was calculated in 25 patients per group. A difference in weight 2kg, standard deviation of 2.5, alpha of 0.05 and power of 0.8 were used.

with the following formula:

$$n = 2S^2 (Z\alpha + Z\beta)^2$$

$$\Delta^2$$

Allowing to detect this difference with power of 80% (error  $\beta = 0.20$ ) and with an alpha error of 5%

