#### **36. Procedures for the withdrawal of a patient from the study**

- Removal of data obtained through patient participation
- Valuation by medical specialists of the department.
- Assessment by department nutritionist.
- A conventional food plan is given.

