#### **43. Recruitment potential (number of subjects to be recruited)**

25 subjects for a diet in 3 meal times.

25 subjects for a diet in 6 meal times.

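### The stated 80% power holds only if all 25 randomised patients per arm are analysed; recruitment has no reserve, although the protocol's own rules remove patients and their data

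*Protocol*

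**What the plan says.** **Sample size (Protocol sections 27 and 42, same text).** "The calculation of the sample size was carried out taking as main outcome the body weight". The inputs are explicit: "A difference in weight 2kg, standard deviation of 2.5, alpha of 0.05 and power of 0.8 were used". The result is that "the sample size was calculated in 25 patients per group", with the closing claim "Allowing to detect this difference with power of 80" per cent. The printed formula has no term for losses, and neither section adds one.

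**Recruitment (sections 43 and 33).** Section 43 gives "25 subjects for a diet in 3 meal times" and the same number for six meal times. The randomisation list in section 33 is a single block of 50, with 25 entries for each arm. It has no spare slots, and no replacement of eliminated patients is stated.

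**Removal (sections 35, 36 and 38 c).** Section 35 lists grounds for premature withdrawal. Section 38 c lists four elimination criteria: unwillingness to continue, "Individuals who do not tolerate the placement of the MCGI", not following the meal plan, and not keeping to the assigned meal times. Among the steps for a withdrawn patient, section 36 lists "Removal of data obtained through patient participation".

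**The concern.** A sample size formula of this kind returns the number of patients who contribute an outcome to the test. The protocol uses that number as the number recruited as well, and then sets out several ways in which a recruited patient, and that patient's data, can leave the analysis. The power statement and the removal rules therefore fit together only if the rules are never applied.

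What is at stake is how the weight result is read. If patients are removed, a non-significant difference would be set against a stated 80% power that the analysed sample does not have. Readers would then give the trial more credit for ruling out a 2 kg difference than it has earned.

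**Working it through.** **Inputs, all from sections 27 and 42.** Difference Δ = 2 kg; S = 2.5 kg; alpha = 0.05; power = 0.80. The sidedness of alpha is not stated and is settled in step 1.

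**Step 1: reproduce the plan's figure.** The formula is n = 2S²(Zα + Zβ)²/Δ².

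- Two-sided alpha: 2 × 6.25 × (1.960 + 0.842)² / 4 = 24.53, rounded up to 25 per arm. This is the plan's figure.
- One-sided alpha: 19.32, rounded up to 20 per arm. This is not the plan's figure.

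So the plan used two-sided alpha and made no inflation for losses. The only slack is the rounding from 24.53 to 25.

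**Step 2: compare needed with recruited.** Needed for analysis: 25 per arm. Recruited (section 43): 25 per arm. Allocation slots (section 33): 50, as 25 and 25. Reserve: 25 − 25 = 0 per arm.

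**Step 3: power if fewer are analysed.** Two methods are shown so that the effect of losing patients is not confused with the effect of changing method.

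- Plan's normal approximation: power = Φ(Δ/SE − 1.960), with SE = S√(2/n). At n = 25, SE = 2.5 × √0.08 = 0.7071, Δ/SE = 2.828, and power = Φ(0.868) = 80.7%.
- Exact t-test: noncentral t with 2n − 2 degrees of freedom and noncentrality Δ/SE. Student's t is one of the two tests that section 41 names for comparing the groups.

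The difference detectable with 80% power is (1.960 + 0.842) × SE under the normal approximation, and is solved numerically for the exact t.

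| Analysed per arm | Lost of 25 | Power, normal | Power, exact t | Detectable, normal | Detectable, exact t |
|---|---|---|---|---|---|
| 25 | 0 | 80.7% | 79.1% | 1.98 kg | 2.02 kg |
| 24 | 1 (4%) | 79.1% | 77.4% | 2.02 kg | 2.07 kg |
| 23 | 2 (8%) | 77.4% | 75.6% | 2.07 kg | 2.11 kg |
| 22 | 3 (12%) | 75.6% | 73.6% | 2.11 kg | 2.16 kg |
| 20 | 5 (20%) | 71.6% | 69.3% | 2.21 kg | 2.27 kg |

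The loss rate is not in the document, so the rows below 25 are an assumed range. Every row takes losses as equal in the two arms and unrelated to outcome, with the 2 kg difference and the SD of 2.5 unchanged.

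**Step 4: separate the two effects.** At 25 per arm, moving from the normal formula to the exact t costs 80.7 − 79.1 = 1.6 points with nobody lost. Going from 25 to 20 analysed costs 80.7 − 71.6 = 9.1 points by the plan's own formula and 79.1 − 69.3 = 9.8 points by exact t. Most of the shortfall at 20 per arm therefore comes from losing patients, not from the choice of method.

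**The case against.** The best defence is that nothing is miscalculated. The formula, its inputs and the result of 25 agree, and the stated 80% is accurate for 25 analysed patients per arm. This stands. The fault is a missing allowance for losses, not an arithmetic error. The 1.6-point gap between the normal formula and the exact t at 25 per arm is a matter of method and should not be counted against the plan.

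Second, the document says what happens when a patient meets an elimination criterion, not how many will. A reader might infer that the protocol expects losses, or that the analysed number is certain to fall below 25. The text supports neither. It supports only that removal is provided for and that no margin covers it. One loss per arm costs less than two points.

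Third, two of the four elimination grounds in section 38 c concern adherence. Removing such patients could change the between-arm difference and the SD in either direction, so the tabulated power is a guide under stated assumptions and not a forecast. This also stands.

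Finally, section 26 counts an effect of the three-meal plan that is equal to or worse than the six-meal plan as failure. A reader might infer that overstated power leads directly to a wrong negative conclusion. Section 26 does not support that: it judges success on a list of outcomes and mentions neither power nor a non-significant weight test. Treating non-significance as equality would be a mistake at a true 80% power too.

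**Conclusion.** The point holds as a missing reserve. The 25 per arm is correctly derived as the number to be analysed, the same 25 is the number recruited, and the protocol's rules allow patients and their data to be removed without allowance or replacement. The 80% is conditional on zero losses, and sections 27 and 42 do not say so.

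The shortfall is small for one or two losses per arm and material at five: about 72% by the plan's formula, or 69% by exact t, at 20 analysed per arm. At that point the exact-t type II error is 100 − 69.3 = 30.7%, against the stated 20%. These sizes rest on an assumed number of losses, on losses unrelated to outcome, and on the planned difference and SD. The direction does not depend on the rate: under the same assumptions, every loss lowers power.

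The bias from removing non-adherent patients after randomisation is a separate matter. Neither a larger sample nor a restated power corrects it.

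**What to change.** In sections 27 and 42:

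- State that 25 per arm is the number randomised, and that 80% power for 2 kg applies only if all 25 per arm are analysed.
- State the sponsor's own expected analysable number per arm, with its basis.
- Restate the power and the detectable difference for that number, and name the method used. For illustration only: at 20 to 22 analysed per arm, exact-t power for 2 kg is about 69% to 74%, and the difference detectable with 80% power is about 2.2 to 2.3 kg. The range of 20 to 22 is not from the document and should not be copied in place of the sponsor's figure.
- Read a non-significant weight result against the restated figures.

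The cost is a few sentences and a less favourable stated power. No extra patients are needed and no clinical rule changes. If the sponsor would rather keep 25 analysed per arm, recruitment would be 25/(1 − d) for an expected loss d: 25/0.90 = 27.8, so 28 per arm, at an assumed 10%; 25/0.80 = 31.25, so 32 per arm, at an assumed 20%. That would also require extending the 50-slot list.
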